Measured from admission to ICU until the decision to discharge is ordered.

- Reduction of VAE According to the definition from the latest CDC.
- Decrease in ventilation days.

Evaluated by the number of hours of etCO2 from the hospital electronic records

- Decrease in workload related to nurse GRV time.

Patient GRV information obtained through the hospital's electronic records and the usability questionnaires, will be analyzed to determine (a) the estimated nursing time that was expended for GRV activities, and (b) the amounts of GRV removed from the patient.

- Convenience of use of the system and the user interface (by subjective staff questionnaire)

Evaluated via questionnaires filled by physician users and nurse users participating in the study.

- Assessment of urine flow monitoring related to patient condition and usability

Patient lab results obtained through the hospital's electronic records and the usability questionnaires, will be analyzed against smART+ system urine alerts, to determine if the alerts will be useful in diagnosis and usability satisfaction.

 ART MEDICAL PATIENT SAFETY TECHNOLOGY	Number: CRO-C-2822	Date issued: 01-Mar-2021
	Rev.06	Page 16 of 35
Subject: smART Plus Comparative Study Protocol - Beilinson		

3. Study Design

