5.2.9. Staff Questionnaires - group A

At the end of the study, staff will be required to complete a usability questionnaire assessing the convenience of using the system and the user interface. Two different questionnaires will be used for either physician users and nurse users participating in the study. The questionnaires will include a variety of questions such as YES/NO, open-ended and scoring-based questions.

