5.3.5. Data recording- group B

The following information will be acquired from the patient's medical chart (recorded in the hospital sources) for each patient:

- Initial screening: as detailed in the study eCRF
- Feeding information: Food types, amounts, rate, water delivery, parenteral nutrition, TPN, Indirect calorimeter and other nutritional data.
- Gastric residual volume: discard gastric residuals amount, GRV procedure times.
- Medications provided: as detailed in the study eCRF.
- Lab results: all patient lab results ordered during the study as well as all available lab results obtained 24 hours prior to study enrollment and added to the eCRF.
- Imaging: patient imaging (X-rays, CT, and alike) performed during the study should be obtained and added to the eCRF.
- Urine monitoring: amounts, rates, times, warnings and all data related to urinary output and diagnosis, and found in the hospital source.
- ICU submission and discharge ordering times
- Breathing data reports starting from the ICU admission (FiO2, PEEP)
- Demographics

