- The two-sample T-test or Non-parametric Wilcoxon-Mann-Whitney Rank sum test for independent samples (as is appropriate) will be applied for testing the statistical significance of the difference in the estimated nursing time that was expended for GRV activities, and the amounts of GRV removed from the patient between the study groups.
- Convenience of use of the system and the user interface scores (by subjective staff questionnaire) will be summarized in an appropriate table by study group
- The two-sample T-test or Non-parametric Wilcoxon-Mann-Whitney Rank sum test for independent samples (as is appropriate) will be applied for testing the statistical significance of the difference in the assessment of urine flow monitoring related to patient condition and usability between the study groups.
- The two-sample T-test or Non-parametric Wilcoxon-Mann-Whitney Rank sum test for independent samples (as is appropriate) will be applied for testing the statistical significance of the difference in ICU length of stay (measured from admission to ICU until the decision to discharge is ordered) between the study groups.
- Chi-square test or Fisher's Exact test (as is appropriate) will be applied for testing the statistical significance of the difference in percent of subjects experiencing Ventilation associated events between the study groups.

9.2.5 Safety:

Adverse events will be coded using the Medical Dictionary for Regulatory Activities (MedDRA, most updated version) terminology and presented in tables by System Organ Class (SOC) and Preferred Term (PT).

Subject: smART Plus Comparative Study Protocol - Beilinson

AE data will be listed individually and summarized by SOC and by PT within a system organ class for each study group.

Frequency of TEAEs (Treatment-Emergent Adverse Events) and device-related adverse events will be summarized in tables by SOC, PT and study group and by seriousness.

Chi-square test or Fisher's Exact test (as is appropriate) will be applied for testing the statistical significance of the difference in percent of subjects experienced any AE, drug-related AE and SAE between the study groups.

Concomitant medications entered into the database will be coded using the World Health Organization (WHO) Drug Reference List, which employs the Anatomical Therapeutic Chemical classification system.

10. Regulatory, Ethical, and Study Oversight Considerations

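### Nursing GRV time is tested between groups, but one of its two stated sources is a usability questionnaire whose only defined procedure is for group A

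*Combined protocol and SAP*

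**What the plan says.** Reduced nurse workload for GRV is a named secondary endpoint. Section 2.2 gives its derivation in one sentence, which joins GRV data from electronic hospital charts with a second source: "the usability questionnaires, will be analyzed to determine (a) the estimated nursing time that was expended for GRV activities".

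The only questionnaire procedure in the protocol carries the heading "5.2.9. Staff Questionnaires - group A". It takes place once the study ends, and its scope is put this way: "staff will be required to complete a usability questionnaire assessing the convenience of using the system and the user interface". It exists in two forms: "Two different questionnaires will be used for either physician users and nurse users participating in the study".

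Section 9.2.3 applies a two-sample t-test or a Wilcoxon-Mann-Whitney test to this quantity: "difference in the estimated nursing time that was expended for GRV activities, and the amounts of GRV removed from the patient between the study groups". Section 9.2.1 sets significance at 5%, two-tailed.

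For group B, section 5.3.5 lists among the chart data "Gastric residual volume: discard gastric residuals amount, GRV procedure times". Section 5.2.8 has the same chart item for group A. No questionnaire appears anywhere in 5.3.1 to 5.3.5.

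**The concern.** A two-group test of nursing time is interpretable only if the time is obtained in the same way in both groups. Here one of the two named sources has a defined procedure in one group only. That source is subjective, is about the device, and comes from staff who know the allocation, because section 5.1 makes the trial open-label. Randomization balances patients between arms. It does nothing about a difference in how the outcome is measured.

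At stake is whether a significant result on this endpoint could be read as a change in nursing workload, or only as a change in workload mixed with a change in data source. The plan gives no rule that would let a reader separate the two.

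**Working it through.** The documents give no effect size, SD or power for this endpoint. Section 9.1 sizes only feeding efficiency, ventilation days, ventilator-associated events and length of stay. The check is therefore mainly a comparison of sections.

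**Step 1. Sources by arm**

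| Source | Group A | Group B |
|---|---|---|
| Chart GRV amounts and procedure times | yes (5.2.8) | yes (5.3.5) |
| Console GRV amounts and times | yes (5.2.8, data recorded by the console) | none |
| Staff usability questionnaire | yes (5.2.9) | no procedure in 5.3 |
| Questionnaire row in the Schedule of Activities (5.5) | none | none |

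Section 2.2 names the first and third rows as the basis for nursing time. Only the first is defined for both arms.

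**Step 2. Can the questionnaire supply the tested quantity?** It is completed by staff at the end of the study, and its described content is convenience of the system and its interface. No time item is described. A two-sample test needs one value per patient, and no section says how chart records and staff answers become such a value.

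**Step 3. Text pointing the other way.** Section 9.2.3 tabulates the convenience scores per study group, which suggests questionnaires in both arms. Section 2.2 refers to physician and nurse users in the study without limiting them to one arm. Set against 5.2.9, 5.3 and the Schedule of Activities, this is an internal conflict. Collection in group A only is the likelier reading, but it is not settled.

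**Step 4. What a source difference could do to the test.** This is an illustration, and the shift is assumed. Let d be a mean difference, in SD units, that arises only from the data source, with no true difference in nursing time. For a two-sample t-test with n per group:

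- df = 2n − 2, noncentrality = d × √(n/2)
- rejection probability = P(|T| > t(0.975, df)), where T is noncentral t

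The formula reproduces the plan's nearest figure. With d = 0.46 and n = 100, the noncentrality is 0.46 × √50 = 3.25 and the power is 89.9%, against the 90% stated in 9.1 for ventilation days and length of stay.

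Applied to a source-only shift at two-sided 5%:

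| Assumed shift (SD) | Noncentrality, n = 100 | P(significant), n = 100 | Noncentrality, n = 50 | P(significant), n = 50 |
|---|---|---|---|---|
| 0 | 0 | 5.0% | 0 | 5.0% |
| 0.1 | 0.71 | 10.8% | 0.50 | 7.9% |
| 0.2 | 1.41 | 29.1% | 1.00 | 16.8% |
| 0.3 | 2.12 | 56.0% | 1.50 | 31.8% |

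The 100 per group is the full-study target, and 50 per group is the synopsis target for the Beilinson site. The probabilities are the same for a shift in either direction.

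**The case against.** The strongest reply is that the documents do not show the two arms being measured differently. They show an undefined derivation. No combination rule is given, the questionnaire items are not reproduced, and the respondents are staff. Section 5.1 asks for balance between arms at each site, so the same nurses may look after patients in both groups. One questionnaire could then, in principle, ask about manual and device GRV alike. The tabulation per study group in 9.2.3 fits that reading.

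Much of this stands, and it limits what can be claimed. A reader might infer that group A's value will be a blend of charts and opinion while group B's is chart only, and that the resulting bias favours the device. The documents support neither step. The first needs a combination rule that is not written. The second needs a direction that nothing in the plan establishes.

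The reply does not remove the point. The plan still names, as an input to a two-arm test, an instrument for which it defines a procedure in one arm only, and its own sections disagree on who completes it. That is more than missing detail, because following the plan as written permits an asymmetric measure.

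Two further objections bear on the remedy. The charted procedure times may be clock times and not durations, in which case neither chart yields minutes. And because the device handles GRV through a hub-controlled line (1.3) described as automatic (1.8.1), any benefit may lie in less nurse time per procedure. Assigning the same minutes per procedure to both arms would erase that benefit by construction. Both objections are correct, and the fix takes account of them.

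**Conclusion.** The concern holds in this form: the between-group test of nursing GRV time can include a difference in data source between the arms, and the passages on questionnaire coverage must be reconciled before the test can be interpreted. This rests on reading 5.2.9, 5.3 and the Schedule of Activities as the operative description of who completes questionnaires.

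The direction and size of any distortion are unknown. The rejection probabilities above show only how sensitive the test would be to assumed shifts, and do not estimate what will happen in this trial.

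The consequence is confined to one secondary endpoint that section 9.1 does not size. The primary endpoint and the sized secondary endpoints are unaffected. It should be corrected before the data are analysed.

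**What to change.** In 2.2 and 9.2.3, base the between-group test only on a per-patient measure taken from the same source in both arms, namely the chart GRV procedure records listed in 5.2.8 and 5.3.5:

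- If the chart records procedure durations, use those in both arms. State that they mean nursing time: section 1.1.3 describes passive drainage over two hours at some sites, and that is not two hours of nursing.
- If it records only clock times, use the number of charted GRV procedures requiring a nurse, and label it a procedure count, not minutes. State how that is decided in group A, where the device handles GRV, because it is not a listed chart field.

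Keep questionnaire answers descriptive and outside the test. Reconcile the tabulation per study group in 9.2.3 with 5.2.9, 5.3 and the Schedule of Activities. Group A console GRV times should also stay out of the tested measure, since group B has no counterpart.

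**Cost.** This needs wording changes, plus a check of what the chart GRV field actually contains. The chart data are already planned for both arms. The drawback is that a count does not capture any change in nurse time per procedure. Capturing that would need the same time item collected in both arms and added to 5.3 and the Schedule of Activities, which is new data collection.

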3.1. Overall Design

The design of the study is as follows:

- Comparative: 2 groups. 100 participants per group
- Interim statistical analysis: planned after 50 patients
- Random: the randomization is controlled by APACHE score
- Multi-site: Israel, United States, Europe

3.2. End of Study Definition

A participant is considered to have completed the study if he or she has completed all phases of the study including the last scheduled procedure shown in the Schedule of Activities (SoA).

In addition, participant is considered to have completed the study if he/she is no longer required enteral feeding (due to feeding tube removal, medical order, or any other reason which feeding stopped and is not scheduled to be renewed within the 14 days of study duration).

4. Study Population

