1.8.2. Known potential benefits

Subject: smART Plus Comparative Study Protocol - Beilinson

As explained above, the various components of the smART+ System must operate as a cohesive system in order to allow feeding optimization as demonstrated in the flowchart below. With validation of the smART+ features during the study, the clinical benefit of the device will be the lowering of risks associated with tube displacement and malpositioning as well as lowering the risks associated with reflux and aspiration.

In addition, the smART+ System is able to continuously measure the patients REE and minimize the risk of overfeeding. Therefore, by reducing overfeeding it not only achieves feeding optimization, but it also reduces the likelihood of reflux episodes due to overfeeding.

2. Objectives and Endpoints

2.1. Primary Endpoint:

 ART MEDICAL PATIENT SAFETY TECHNOLOGY	Number: CRO-C-2822	Date issued: 01-Mar-2021
	Rev.06	Page 15 of 35

Subject: smART Plus Comparative Study Protocol - Beilinson

Optimization of the delivery of nutrition by the smART+ System as compared to standard of care, by automatically calculating and administering enteral feeding better than standard of care (REE or Calorimeter).

Optimization is defined as the ability of the system to provide adequate nutrition (not overfeed or underfeed) when compared to treatment via standard of care.

Evaluation will be conducted based on an analysis and comparison of the following parameters (obtained through the hospital's electronic records for control group and smART+ records for the treated group):

- Patient caloric target set
- Volume of patient nutritional intake value versus actual patient need – this is calculated by assessing the actual nutrition delivered, discarded nutrition in the GRV bags as well as the unused quantity in discarded feed bottles (if applicable).

As part of optimization evaluation, feeding efficiency calculation ((Net nutrition delivered [ml])/ (VTBD [ml])) should be calculated for the days when the patient received enteral feeding that given under medical order, removed from the patient, or stopped feeding that was not renewed until the end of the study. Feeding efficiency should not be calculated for the days that patient has been discontinued from enteral feeding by a medical order.

2.2. Secondary Endpoints:

- Safety

Safe use of the entire system will be assessed based on the occurrence of device related AE or SAE.

- Decrease in ICU length of stay.

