4.3. Warnings

- Participants may not receive any kind of nutrition given NOT through the feeding tube (or one of its ports)
- MRI- the Feeding tube should be removed before performing the procedure.
- CPR- the feeding tube should NOT be disconnected from the Hub before performing the procedure.

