5.2.3. Feeding insertion- group A

Study staff should follow the device instructions for use and specific instructions provided by the console during initial tube placement. Time of tube placement is recorded by the console. Once initial placement is confirmed by the system, verification of correct placement should

 ART MEDICAL PATIENT SAFETY TECHNOLOGY	Number: CRO-C-2822	Date issued: 01-Mar-2021
	Rev.06	Page 19 of 35

Subject: smART Plus Comparative Study Protocol - Beilinson

be performed according to hospital procedures (such as abdominal /chest X-ray /other gold standard).

5.2.4.Vital signs- group A

Vital signs (e.g., temperature, pulse, respirations, blood pressure) should be noted within 10 minutes of feeding tube insertion.

5.2.5.REE measurement- group A

Once the patient has recovered from the process of inserting the feeding tube, a baseline REE measurement should be taken using the smART+ flow sensor and CO₂ sensor.

5.2.6.Feeding program- group A

Once the REE measurement is accomplished, personnel authorized by the hospital should program a suitable feeding program using the smART+ Console and in accordance with hospital procedure.

5.2.7.Ongoing use- group A

If system alerts of tube displacement during ongoing use, the need for tube reinsertion/repositioning should be evaluated and performed as needed.

If system alerts an increase in REE, the message should be evaluated by personnel authorized by the hospital, who should decide if to change the patient's feeding program.

5.2.8.Data recording- group A

The following information will be acquired from the patient's medical chart (recorded in the hospital sources) into the eCRF, for each patient

- Initial screening: as detailed in the study eCRF
- Feeding information: Food types, amounts, rate, water delivery, parenteral nutrition, TPN, other nutritional data
- Gastric residual volume: discard gastric residuals amount, GRV procedure times.
- Medications provided: as detailed in the study eCRF.
- Lab results: patient lab results, as detailed in the study eCRF, and obtained 24 hours prior the feeding tube insertion and during the study, should be recorded in the eCRF.
- Imaging: (X-ray, CT, and alike) performed during the study should be obtained and attached to the eCRF.
- Urine: amounts, rates, times, warnings
- ICU submission and discharge ordering times
- Breathing data reports starting from the ICU admission (FiO₂, PEEP)
- Demographics

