7.1. Participant Discontinuation/Withdrawal from The Study

Each subject (or delegate) will be informed of his/her right to withdraw from the study at any time and for any reason. The Investigator may withdraw a subject from the study at any time if he considers that remaining in the study compromises the subject's health.

Additional criteria for discontinuation/withdrawal:

- The insertion of the feeding tube has failed after 3 attempts in each nostril
- Disease progression which requires discontinuation of the study intervention
- If the participant meets an exclusion criterion (either newly developed or not previously recognized) that precludes further study participation.

In the event a subject discontinuation/withdraws from the study the following procedures will be observed:

- The reasons for any subject discontinuation/withdrawal will be recorded on the study completion form of the eCRF.
- The investigator will inform the sponsor of the subject's early withdrawal for any reason.
- If withdrawal is caused by an adverse event that the investigator considers may be related to the device, it will be reported to the IRB and to the Sponsor.

Subjects who signed the informed consent form and are randomized but do not receive the study intervention are considered screen failures and may be replaced. Subjects who sign the informed consent form, and are randomized and receive the study intervention, and subsequently withdraw, or are withdrawn or discontinued from the study may also be replaced.

 ART MEDICAL PATIENT SAFETY TECHNOLOGY	Number: CRO-C-2822	Date issued: 01-Mar-2021
	Rev.06	Page 25 of 35

Subject: smART Plus Comparative Study Protocol - Beilinson

In addition, this study may be temporarily suspended or prematurely terminated if there is sufficient reasonable cause.

Circumstances that may warrant termination or suspension include according to the PI decision, but are not limited to:

- Determination of unexpected, significant, or unacceptable risk to participants
- Demonstration of efficacy that would warrant stopping
- Insufficient compliance to protocol requirements
- Data that are not sufficiently complete and/or evaluable
- Determination that the primary endpoint has been met
- Determination of futility

Study may resume once concerns about safety, protocol compliance, and data quality are addressed, and satisfy the sponsor, IRB and/or Food and Drug Administration (FDA).

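### Group A days fed by standard equipment fall within the primary endpoint but have no usable data source in section 2.1, so treated-arm feeding efficiency tends towards efficiency while on the device

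*Combined protocol and SAP*

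**What the plan says.** **Which days count.** Section 2.1 says that feeding efficiency (net nutrition delivered divided by VTBD, both in ml) "should be calculated for the days when the patient received enteral feeding that given under medical order". It also brings in days when feed was removed or feeding stopped for good. It leaves out only days when a medical order discontinued enteral feeding. No condition refers to the tube or pump in use.

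**Where the values come from.** The same section says that the parameters are "obtained through the hospital's electronic records for control group and smART+ records for the treated group".

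**What else is collected for group A.** Section 5.2.8 has chart data entered in the eCRF for each treated patient, including "Feeding information: Food types, amounts, rate, water delivery, parenteral nutrition, TPN, other nutritional data" and discarded gastric residuals. Section 5 treats both the chart and the smART+ System as source data. The Nutrition camera, which measures unused feed, is described only for group B (5.3.1). The group A camera is placed near the patient's head and is optional (5.2.1).

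**Status when the tube comes out.** Section 3.2 counts as completed a participant who is "no longer required enteral feeding (due to feeding tube removal, medical order, or any other reason which feeding stopped". A second condition in that sentence concerns resumption: "and is not scheduled to be renewed within the 14 days of study duration". Section 4.3 foresees a removal that need not end feeding: "MRI- the Feeding tube should be removed before performing the procedure". Section 7.4.1 ends group A adverse event recording at the end of the study, straight after tube removal. Section 7.1 lists failed insertion, disease progression that requires stopping the intervention, and newly met exclusion criteria as grounds for discontinuation. It allows discontinued patients to be replaced.

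**The concern.** Consider a treated patient whose smART+ tube comes out on day 6 and who is then fed through the hospital's own tube and pump. By the day rule in 2.1, the later days belong in feeding efficiency. By the source rule in 2.1, the value should come from smART+ records, which would not hold feed given by other equipment. Nothing in 9.2 or elsewhere sends the 5.2.8 chart data to the primary endpoint for those days.

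The gap is one-sided. A control patient may change tube, pump or feeding method and every fed day remains in the hospital record, which is the designated source. Only in group A does leaving the assigned equipment take fed days out of the designated source. If they are simply lost, the comparison becomes efficiency while on the device in group A against efficiency over all fed days in group B. That favours the device in the very patients in whom it was not kept in use. The trial is open-label, so a handling rule chosen after the data are seen could not be defended as neutral.

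**Working it through.** **1. The passages side by side.**

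| Question | Group A | Group B |
|---|---|---|
| Is a fed day off the assigned equipment in scope (2.1)? | Yes; equipment is not mentioned | Yes |
| Designated source (2.1) | smART+ records | Hospital electronic records |
| Does that source hold the feed given that day? | No | Yes |
| Chart amounts, rate and discarded GRV collected? | Yes (5.2.8), but not linked to the endpoint | Yes (5.3.5) |
| Ordered volume listed as a data item? | Not explicitly | Not explicitly |
| Unused feed measured by camera? | Not described | Yes (5.3.1) |

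The fourth row shows that the gap can be closed. The last two show that it is not closed already, even if an analyst turns to the chart. VTBD is not expanded in the protocol; I read it as the ordered volume.

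**2. The plan's own figure (background).** Section 9.1 gives 50 per group, effect size 0.70, two-sided alpha 0.025 and 90% power.

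- Normal approximation: 0.70 × √(50/2) = 3.50. Subtracting the critical value 2.24 leaves 1.26, which gives power 0.896.
- Noncentral t: 0.888.

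The stated figure is reproduced within rounding.

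**3. Illustrative bias (assumed inputs).** The documents give no off-device rate, no efficiency values and no standard deviation. Assume 10 fed days with equal ordered volume, 6 on the device at 95% and 4 off it at 75%.

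- All fed days: (6 × 0.95 + 4 × 0.75)/10 = 0.87.
- On-device days only: 0.95.
- Shift per switching patient: 0.95 − 0.87 = +0.08.
- Shift in the group A mean: 0.10 × 0.08 = +0.8 points if 10% switch; 0.20 × 0.08 = +1.6 points if 20% switch.

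**4. Does the handling rule matter for power?** These are limiting cases at 50 per group, by noncentral t. They treat a switching patient as having no on-device contribution at all, which overstates the effect for anyone with valid on-device days.

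| Share of group A switching (assumed) | Switchers have no primary value (n in A vs 50) | Switchers kept, with control-like efficiency (effect size) |
|---|---|---|
| 10% | 0.868 (45) | 0.807 (0.70 × 0.90 = 0.63) |
| 20% | 0.844 (40) | 0.699 (0.70 × 0.80 = 0.56) |

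The two rules lead to different analyses. The lower power in the last column is no reason to drop the days: the smaller effect there reflects the system as assigned.

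**The case against.** The strongest reply is that 2.1 does not confine the treated arm to smART+ records, that section 5 makes the chart a source for both arms, and that 5.2.8 collects group A feeding amounts, rate and discarded GRV. A sensible analyst would use the chart for off-device days. This stands to the extent that the days are recoverable. It does not settle the point, because 2.1 names one source per arm, and ordered volume and unused feed are not explicit group A chart items.

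Switching may also be rare. Section 5.2.7 has reinsertion evaluated after a displacement alert, 6.1 has the sponsor supply replacement equipment, and 4.3 does not say that a standard tube follows MRI. All of this is fair. No rate is given in either direction.

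Three stronger readings are tempting, and the documents do not support them:

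- *That such a patient has no valid primary data.* Days on the device are recorded and remain usable.
- *That 3.2 makes the patient a completer, so device failures are filed as completions.* Read in full, 3.2 requires that enteral feeding is no longer needed and is not due to resume, which a still-fed patient does not meet. Group A adverse events are recorded regardless of relationship, and device deficiencies that might have led to an SAE have their own route (7.4). What remains is a risk of misfiling: 3.2 names tube removal as a reason, 4.3 foresees removal for a procedure, and 7.4.1 ties the end of event recording to removal.
- *That off-device days score zero.* In the example this would give 6 × 0.95/10 = 0.57 and move the group mean by −3 to −6 points. No passage imputes zero. The only opening is that, seen through smART+ records alone, such days resemble the permanently stopped feeding that 2.1 counts.

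**Conclusion.** The point holds as an omission in the primary endpoint definition. Group A days or part-days fed by standard equipment are in scope under 2.1 but have no usable designated source, while the corresponding group B days do. Followed as written, 2.1 moves treated-arm feeding efficiency towards efficiency while on the device.

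The size is unknown. About +1 to +2 points on the group A mean is an illustration that rests on assumed efficiencies, an assumed 6/4 split of days, 10-20% switching, and the days being dropped. With no standard deviation in the documents, it cannot be related to the planned effect size of 0.70. The plan should be changed because the gap is one-sided, affects the primary endpoint and is easy to close before data are seen.

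**What to change.** **Section 2.1.** State that, for group A days or part-days not fed through smART+, ordered (VTBD), delivered and discarded volumes come from the hospital record, as for group B. Keep those days in the patient's primary value to the end of participation. Report on-device days as a secondary summary.

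**Section 5.2.8.** Add ordered volume and unused feed to the group A chart items. Say how unused feed is obtained off the device, and that it comes from the chart alone if there is no camera.

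**Sections 3.2, 7.1 and 7.4.1.** Reconcile them so that smART+ removal with continued enteral feeding is recorded as *device discontinued, still in study*, with a reason. At present 7.1 asks for reasons only at discontinuation or withdrawal: "The reasons for any subject discontinuation/withdrawal will be recorded on the study completion form of the eCRF". Event recording under 7.4.1 should then follow the end of participation, as 7.3 already says.

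**Cost.** Wording in these sections, one eCRF status field with a reason, and the added chart items. No clinical rule changes. The treated-arm result may be slightly less favourable, and unused feed will be measured less precisely on off-device days than by the group B camera.
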